#### 6.2.3 *Outcome of Events*

This is the outcome of the SAE. This may differ on initial and follow-up reports of an SAE. The Investigator will indicate the outcome on the initial report (for example unresolved) and update as appropriate on follow-up SAE Forms.

1. Resolved – no sequelae. The condition has resolved completely with no lasting side effects.
2. Resolved – with sequelae. The condition has resolved but a medical condition remains as a consequence of the event (e.g. the subject experiences a stroke the sequelae may be numbness in right/left arm and leg).
3. Unresolved. The condition is still present at the time of the report. Follow-up information should be provided on resolution.
4. Death. Condition prompting SAE resulted in the subject’s death.

If “Resolved – with sequelae” is chosen, the nature of the sequelae must be specified, and a resolution date should be provided. If “Unresolved” is chosen, the resolution date should be left blank. Subjects should be followed up until the event is resolved and a follow-up SAE Form should be provided at this time. Hence, it is anticipated that on the conclusion of an event an outcome other than “Unresolved” would be chosen and a resolution date would be provided. The only exception to this would be:

1. If the event described is classified as a congenital abnormality/birth defect. In this circumstance this should be clearly indicated on the form.
2. If “Death” is chosen, the resolution date will be the date of death. An autopsy report should be provided if available.

#### 6.2.4 *Notifying of Adverse Events*

##### 6.2.4.1 *Responsibilities of the Investigator*

For immediately reportable information (SAEs, overdose, and pregnancy) the investigator must inform the pharmacovigilance department via e-mail or fax using the SAE report within 24 hours of the study site being informed of such event.

##### Adverse Event Reporting Contact:

For this study, the pharmacovigilance department will be the PrimeVigilance Safety Department.

[contact]

E-mail: [[contact]](mailto:[contact])

For any questions regarding safety reporting, the Investigator should reach out to the PrimeVigilance Safety Department using the contact details above. In case of any

urgent queries related to the safety of the subjects involved in the trial, the site should phone the Medical Monitor.

Investigators or other site personnel should inform PrimeVigilance's Safety department of any follow-up information that becomes available for a previously reported SAE immediately but no later than 24 hours of becoming aware of the information. Follow-up reports (as many as required) should be completed and faxed or e-mailed following the same procedure above. Any requested supporting documentation (e.g., electrocardiogram [ECG], laboratory results, autopsy report) should be sent to PrimeVigilance's Safety department.

Prior to forwarding any copies of medical records as supporting documentation for safety reporting, these documents need to be coded in a way that keeps the subject's identity confidential (e.g., by using the subject's identification code, randomization number, etc. and subject personal data blinded – further instructions will be provided by your responsible Monitor).

For fatal and life-threatening SAEs, PrimeVigilance's Safety department will work with the investigator to ensure that any additional information is provided by the investigator within 1 business day. The investigator will ensure that all the necessary information for all other SAEs will be provided within the timelines stipulated by the Sponsor when the request for information is made.

If required, the investigator is responsible for informing local IECs of safety reports in compliance with applicable regulatory requirements. Copies of all correspondence relating to reporting of any safety reports to the IEC should be maintained in the Investigator Site File (ISF).

**Subject Enrolment to the First Administration of IMP:**

Only serious procedure-related AEs will be reported to the Sponsor using the reporting process (SAE report form) as described above.

**After subject's last study visit:**

The investigator will notify PrimeVigilance's Safety Department of any SAE that she or he becomes aware of and considers related to the IMP.

**Following-up AEs / SAEs:**

At the subject's last study visit (including the Early Termination Visit), a Safety Follow-up Visit should be scheduled up to 2 weeks after the final examination only for those subjects who experienced not resolved related AEs or laboratory parameters showing not normalised clinically relevant changes or SAEs. The assessments measured will be determined by the investigator. All data must be documented in the eCRF.

*6.2.4.2 Responsibilities of the Sponsor*

PrimeVigilance's safety department is responsible for fulfilling all obligations regarding notification of Regulatory Authorities and IECs according to applicable regulatory requirements (expedited and periodic reporting, e.g., serious unexpected suspected adverse reactions, Development Safety Update Report). In addition, the Sponsor will provide safety information to investigators according to the current regulations.

**6.2.5 Laboratory Parameters**

During the study, the following estimated total amounts of blood for both safety and PD assessments will be taken.

- All subjects –approximately 130 ml
- Subset analyses:
  - PK sampling rich – an additional 28 ml
  - PGE2 levels in whole blood – an additional 8 ml
  - Platelet activation (FACS) – an additional 12 ml

Laboratory assessments will be performed centrally at the central laboratory by means of their established methods. Before starting the study, the central laboratory will supply PrimeVigilance/the Sponsor with a list of the normal ranges and units of measurement.

Safety laboratory assessments ([Table 6.1](#)) will be conducted on samples collected and analysed by standard laboratory procedures at the time points designated in the Overall Schedule of Assessments (see [APPENDIX 2](#)). Tests that are not done must be reported as such on the eCRFs.

**Table 6.1: Safety Laboratory Assessments**

Clinical chemistry	Haematology	
P/S-Albumin	B-Haemoglobin (B-Hb)	
P/S-Sodium	B-Erythrocyte count (B-EPC)	
P/S-Potassium	B-Ery-Mean Corpuscular Volume (B-MCV)	
P/S-Calcium, total	B-Haematocrit (Erythrocyte volume fraction B-EVF)	
P/S-Glucose	B-Platelet count (B-Thrombocyte particle concentration B-TPC)	
P/S-C-reactive protein (P-CRP)	B-Leukocyte count (B-LPC)	
P/S-Bilirubin, total	B-Leukocyte differential, absolute count (lymphocytes, monocytes, neutrophil-, eosinophil- and basophil-granulocytes)	
P/S Bilirubin – conjugated		
P/S-Uric acid		
P/S-ASAT	HBV	
P/S-ALAT	HCV	
P/S-Cholesterol	HIV	
P/S-Cystatin C	Urinalysis – dipstick semi-quantitatively In event of abnormal findings reanalysis or urine to be sent for further lab analysis if considered clinically relevant by the investigator	
P/S-Creatinine		
eGFR		
P/S-Osmolality		
P/S-Urea or BUN		
U – Creatinine		
P/S-ALP		U – pH
P/S-GT		U – Glucose
P/S-LDH		U – Ketone
S-Electrophoresis		U – Bilirubin
pro-BNP	U – Blood	
Hormone analysis (enrolment only)	FSH test (at enrolment, postmenopausal females only)	
P/S-free T3	P/S-FSH	
P/S-total T4	Drug screen* Standard practice at site (minimally to include alcohol † and cocaine)	
P/S-free T4		
P/S-Thyroid Stimulating Hormone (TSH)		
	Pregnancy test (WOCBP) Urine pregnancy test (minimum sensitivity 25 IU/L or equivalent units of HCG)	

\* To minimally include screening for alcohol and cocaine, but preferably also THC, opioids, barbiturates, and benzodiazepines.

† Subjects are not permitted to consume alcohol from midnight prior to a visit involving cold challenge until the end of that study visit.

### 6.2.6 Vital Signs

Vital signs will be measured and recorded at the time points designated on the Overall Schedule of Assessments (see [APPENDIX 2](#)). The following measurements must be performed: systolic/diastolic blood pressure and pulse. Vital signs will be measured after the subject has been in the supine position for at least 5 minutes. All measurements will be recorded on the vital signs eCRF. Abnormal test results may be repeated at the discretion of the investigator and must be reported on the corresponding eCRF. When vital signs, ECGs, and/or blood sample collection occur at the same time, vital signs should be performed before ECGs and/or blood sample collection.

### **6.2.7 Electrocardiograms**

During the study, 12-lead ECGs will be performed at the time points designated on the Overall Schedule of Assessments (see [APPENDIX 2](#)).

The subject must be in a supine position in a rested and calm state for at least 5 minutes before ECG assessment is conducted. If the subject is unable to be in the supine position, the subject should be in the most recumbent position possible. All ECGs should be performed in a standardised method, in triplicate, and approximately 30 seconds apart, prior to blood draws or other invasive procedures. Each ECG must include the following automatically derived measurements: QRS, uncorrected QT interval (QT), corrected QT, RR, and PR intervals.

The Principal Investigator or designated site physician will review and sign all ECGs. Results must be summarised in writing and classified as normal; abnormal, clinically relevant; or abnormal, not clinically relevant. Once signed, the original ECG tracing will be retained with the subject's source documents. At the request of the Sponsor, a copy of the original ECG will be made available.

### **6.2.8 Physical Examinations**

The investigator or qualified designee will perform a complete physical examination (genitourinary examination not required) at Screening (Visit 1) and Follow-up (Visit 5) and then abbreviated physical examinations at the time points designated on the Overall Schedule of Assessments (see [APPENDIX 2](#)). Pre-dose abnormal findings will be reported on the medical history eCRF. Any adverse change from the baseline physical examination (day 1 examination) will be documented on the AE eCRF. Height will be measured at Screening (Visit 1) only.

A full physical examination will include weight, inspection of general appearance, skin, neck (including thyroid), eyes, ears, nose, throat, heart, lungs, abdomen, lymph nodes, extremities, musculoskeletal system, nervous system and presence or absence of DUs.

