## **8.6 Safety Analyses**

For all subjects the analysis of the safety will be based on the SAS and be primarily descriptive. Frequency tables will be presented for the occurrence of any AEs and subtypes (e.g. serious, related, fatal AEs). Sampling statistics will be provided for physical examinations, vital signs, ECG and safety laboratory measurements.

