**APPENDIX 2: OVERALL SCHEDULE OF ASSESSMENTS**

	Visit 1 Screening Visit	Visit 2 Baseline Visit	Visit 3	Visit 4 EoT Visit	Visit 5 Follow-up or Early Termination Visit*
Activity	Enrolment	Treatment start	Treatment	End of Treatment	Follow-up
Day	-21 to -14	1	15 (±2 days)	28 (-2/+1 days)	42-49
Confirmation of Signed Informed consent	X				
Demographics	X				
Medical and surgical history	X				
Concomitant medication	X	X	X	X	X
Physical examination	X	X a	X a	X a	X
Nailfold capillaroscopy	X b				
Vital signs (BP, heart rate)	X	X	X	X	X
Weight/height	X				X c
ECG	X	X d	X		X
Clin chem and haematology	X	X	X	X	X
Thyroid hormones (free T3/T4, tot T4, TSH)	X				
Urinalysis – dipstick	X	X	X	X	X
SSc-related autoantibodies e	X				
Pregnancy test (WOCBP) f	X	X		X	X p
Inclusion/exclusion criteria	X	X			
Hepatitis B, C, HIV-test	X				
Drug screen g	X	X		X	
eDiary	X h				X i
ASRAP questionnaire (PRO)		X	X	X	X
Global Impression of Change (Subject/Physician)				X	
Adverse events	X	X	X	X	X
Randomisation		X			
IMP administration at site j		X		X	
IMP dispense to subjects		X	X		

	Visit 1 Screening Visit	Visit 2 Baseline Visit	Visit 3	Visit 4 EoT Visit	Visit 5 Follow-up or Early Termination Visit*
Activity	Enrolment	Treatment start	Treatment	End of Treatment	Follow-up
Day	-21 to -14	1	15 (±2 days)	28 (-2/+1 days)	42-49
IMP collection and compliance			X	X	
PK sampling (sparse)		X	X	X	
AA metabolites, and urine creatinine k		X		X	
Blood biomarker sampling l		X		X	
Biobank samples – urine and blood		X		X	
Assessments below will be conducted at pre-selected sites					
Finger temperature		X			
Cold challenge, thermography		X m		X	
PK sampling (rich)				X	
PGE 2 levels in whole blood		X		X	
Platelet activation (FACS) n		X		X	
Microvascular volume (D-OCT)		X o	X	X o	X

\* Also, the Early Termination visit, if applicable.

- Abbreviated examination (minimally to include statement regarding DUs).
- Could be performed at Visit 2 if not feasible at Visit 1.
- Only weight (not height) to be recorded at this visit.
- Two ECG assessments will be performed, one pre- and another 170 min post-IMP administration.
- Analysis of antinuclear antibodies (ANA), Scl-70 antibody (anti-topoisomerase I) and anti-centromere antibodies (ACA)

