**Raynaud's Condition Score: (To be completed EVERY evening)**

[figure not shown]
The Raynaud's Condition Score is your rating of how much difficulty you had with your Raynaud's **TODAY**.

When choosing your score, please consider how many attacks you had and how long they lasted. Please also consider how much pain, numbness, or other symptoms the Raynaud's caused in your fingers (including painful sores) and how much the Raynaud's ALONE affected the use of your hands today.

Please record the score using the scale below that best indicates the difficulty you had today with your Raynaud's condition:

0=No difficulty

10=Extreme difficulty

Thank you for completing your Raynaud's Condition Score today.

---

[figure not shown]

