2.2 Deviations from the trial protocol with regard to statistical analyses

The following deviations from the protocol were identified as being important for the statistical analysis:

Definition of FAS population was changed to include all randomised and treated subjects. And the requirement to have eligible data at visit 4 was removed.

Original text in protocol v4.0: The Full Analysis Set (FAS) includes all subjects who were randomized, received at least one dose of IMP and have evaluable data on the primary endpoint at visit 4.

The revised definition in the SAP: The Full Analysis Set (FAS), consists of all subjects that were randomised and received at least one dose of IMP.

Definition of PK Analysis Set (PKAS) was changed to include GS-248 treated patients only:

Original text in protocol v4.0: The PK Analysis Set (PKAS) consists of all subjects who received at least one dose of IMP within 30 hours before a blood sample for GS-248 bioanalysis was taken.

The revised definition in the SAP: The PK Analysis Set (PKAS) consists of all subjects who received at least one dose of GS-248 within 30 hours before a blood sample for GS-248 bioanalysis was taken.

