4.6 Medical history, physical examination

Medical history will be coded with the latest available version but not older than 23.1 Medical Dictionary for Regulatory Activities (MedDRA) and summarized by System Organ Class, Preferred Term, treatment group with counts and percentages for the FAS. A subject will only be counted once in a System Organ Class and a System Organ Class/Preferred Term combination.

All medical history and physical examination (full and abbreviated (digital ulcer statement)) data will be listed.

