- A summary of the number of events (TEAEs) by treatment group, SOC and PT
- A summary of the number and percentage of subjects reporting a TEAE by treatment group, SOC and PT
- A summary of the number of TEAEs by treatment group, intensity and PT
- A summary of the number and percentage of subjects reporting a TEAE by treatment group, intensity and PT
- A summary of the number and percentage of subjects reporting a TEAE by treatment group, relationship and PT
- A summary of the number of subjects reporting a TEAE with a frequency of $\geq 2\%$ by treatment group and PT
- A summary of the number and percentage of subjects reporting a non-serious adverse event occurring in greater than 5% of subjects by treatment group, SOC and PT

TEAE summaries will be ordered in terms of international order of SOC, and alphabetically for PT within SOC.

For the summary of TEAE with a frequency of $\geq 2\%$ TEAEs will be ordered by decreasing frequency.

For each subject and each AE, the worst intensity recorded will be attributed and used in the by-intensity summaries. Similarly, the worst relationship will be attributed and used in the by-relationship summaries.

All adverse events (i.e. TEAEs as well as non-treatment emergent events) will be listed in section 16.2 of the CSR. However, only TEAEs will be summarized in the tables.

AE listings will be presented by treatment group and will include: subject identifier, treatment, age, sex, race, AE (PT and verbatim term), study day of onset, duration, intensity, seriousness, action taken, relationship, outcome and concomitant medication given (including CM number).

Statistical Analysis Plan	Version 2.0		Page 27 of 28
Sponsor	Gesynta Pharma AB	Protocol No	GS-2001

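### The protocol promises by-arm summaries of examination data, but the SAP only lists digital ulcer status and does not declare the change, so ulcer status by visit and late-starting ulcers go untabulated.

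*Protocol*

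**What the plan says.** **Collection.** Protocol 6.2.8 places a full physical examination at Visits 1 and 5, and its content ends with "nervous system and presence or absence of DUs". For Visits 2, 3 and 4 the footnote to the schedule in Appendix 2 specifies an "Abbreviated examination (minimally to include statement regarding DUs". DU status is therefore recorded five times per subject. The Visit 2 check is before dosing (Appendix 3).

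**Protocol commitment.** Section 8.6 states: "Sampling statistics will be provided for physical examinations, vital signs, ECG and safety laboratory measurements". Section 8.2 sets the general rule of sampling statistics for quasi-continuous data and frequency tables for discrete and ordinal data, split by treatment group.

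**SAP.** Section 4.6 states: "All medical history and physical examination (full and abbreviated (digital ulcer statement)) data will be listed". Section 2.2 opens with "The following deviations from the protocol were identified as being important for the statistical analysis" and then names two changes, the definitions of the Full Analysis Set and of the PK Analysis Set. Neither the handling of examination data nor the treatment-emergent window is mentioned.

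**Adverse event route.** Protocol 6.2.8 adds: "Any adverse change from the baseline physical examination (day 1 examination) will be documented on the AE eCRF". SAP 8.1 then provides "A summary of the number and percentage of subjects reporting a TEAE by treatment group, SOC and PT". The same SAP section counts events up to 7 days after last dose as treatment-emergent and tabulates only those; other events are listed.

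**The concern.** DU status is a visible vascular outcome in this disease. The protocol uses it as an entry criterion (exclusion 11) and checks it throughout, but the SAP turns it into a listing. A listing gives no count by arm, no number assessed and no course over visits.

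DU status also helps in reading other results. The Raynaud's Condition Score, a key secondary endpoint, tells subjects to consider hand symptoms "including painful sores", whereas the ASRAP instructions ask them to try to leave sores out. If the two measures diverge, a by-arm DU table is the first thing a reader would want. In the cold challenge (protocol Appendix 5) a hand with a DU is not immersed, so the protocol itself expects some ulcers on study.

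At stake is a descriptive safety summary that the protocol leads the reader to expect. No endpoint, hypothesis test or sample size depends on it.

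**Working it through.** The plan states no figure for DUs, so there is none to reproduce. The check follows each route by which a DU could reach a by-arm table, and then the dates.

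**Routes**

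1. *Ulcer present before dosing.* Protocol 6.2.8 sends pre-dose abnormal findings to medical history, which SAP 4.6 summarises by treatment group, SOC and preferred term. It is counted by arm as a coded term, not as DU status at Visit 2.
2. *New or worse ulcer, starting on treatment or up to 7 days after last dose.* It goes to the AE eCRF and the by-arm TEAE tables, provided the site follows 6.2.8. Counted by arm.
3. *Ulcer starting more than 7 days after last dose, found at Visit 5.* Treatment-emergent under protocol 6.2.1.1 (first dose to last study visit), but not under SAP 8.1. Listed only.
4. *DU present or absent at each visit, with the number assessed.* No table in the SAP. Listed only.

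**Dates.** Inputs: last dose on Day L = 28 (-2/+1), that is Day 26 to 29; Visit 5 on Day 42-49; SAP window of 7 days.

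| Last dose L | SAP window closes, L + 7 | Visit 5, days after last dose | Days after window, 42 - (L + 7) to 49 - (L + 7) |
|---|---|---|---|
| 26 | Day 33 | 16 to 23 | 9 to 16 |
| 28 | Day 35 | 14 to 21 | 7 to 14 |
| 29 | Day 36 | 13 to 20 | 6 to 13 |

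For the nominal last dose on Day 28, the untabulated stretch is 7 of 14 days (50%) to 14 of 21 days (67%) of off-drug follow-up. It is the same for early withdrawals, whose Visit 5 is also 2 to 3 weeks after last dose. This takes the SAP window as referring to onset, as its rule for missing dates does. The SAP's main sentence speaks of events being reported; taken literally, any ulcer first reported at Visit 5 would fall outside, and the gap would be wider.

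**Volume.** With 80 subjects, 80 x 4 = 320 planned DU checks fall at Visits 2 to 5. Of these, 80 x 3 = 240 come after first dosing, including 80 at Visit 5.

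**What a by-arm table could show.** The documents give no DU rate, so the rates here are assumptions. With n = 40 per arm and two-sided 0.05, power = Φ[(d - 1.96·√(2p̄(1-p̄)/n)) / √((p1(1-p1)+p2(1-p2))/n)], where d is the difference and p̄ the average rate.

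- 5% against 10%: Φ[(0.05 - 0.1154)/0.0586] = 13%
- 5% against 15%: Φ[(0.10 - 0.1315)/0.0661] = 32%
- 5% against 25%: Φ[(0.20 - 0.1565)/0.0766] = 71%

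Such a table would be descriptive and could not serve as a meaningful test.

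**The case against.** A reader might infer that new ulcers are never compared between arms. The documents do not support that: routes 1 and 2 both end in tables by treatment group, and route 2 covers all of the treatment period. A reader might also object that healing is never shown. No table shows it, but subjects with an active DU in the 4 weeks before Visit 1 are excluded, so a row for ulcers present at Visit 2 and gone by Visit 4 could hold only those arising in the 2 to 3 week run-in. For ulcers reported as AEs, the AE listings give duration and outcome.

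Four further arguments deserve an answer.

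- *Protocol 8.6 may not promise a DU table.* Sampling statistics are the protocol's term for quasi-continuous data. The obvious such item in the examination is weight, which SAP 8.3 summarises. This stands for 8.6 read alone. Section 8.2 fills the gap for discrete data, although it is a general rule.
- *SAP 4.6 does not say listing only, and the full output list is a separate document (SAP Appendix 1).* A DU table may be planned there. But the same SAP section specifies both a summary and a listing for medical history, and only a listing for examinations.
- *SAP 2.2 covers only changes judged important.* True, so the omission may have been deliberate. The reader still cannot tell.
- *Sores are part of what the Raynaud's Condition Score measures, so a DU table would not alter its analysis.* This stands; the table would only help interpretation.

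**Conclusion.** The point holds as a small, undeclared mismatch between protocol and SAP. DU status by visit is not tabulated by arm. An ulcer starting more than 7 days after last dose and found at Visit 5 is only listed, although the protocol counts it as treatment-emergent. For a last dose on Day 28, that leaves the last 7 to 14 days before Visit 5 without a table.

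The conclusion assumes that sites report adverse changes as 6.2.8 requires, that the SAP window refers to onset, and that the separate output list adds no DU table. The second window problem applies to every adverse event, not to ulcers alone.

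The documents do not support the inference that the plan hides ulcers from between-arm comparison, or that it needs a significance test for them. DU is not an endpoint, no rate is given, and protocol 8.6 makes the safety analysis primarily descriptive.

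**What to change.** 1. In SAP 4.6, replace the listing-only rule with one descriptive table by arm on the Safety Analysis Set: DU present or absent at Visits 2, 3, 4 and 5 with the number assessed; shift from Visit 2; and subjects with a new DU, defined as absent at Visit 2 and present at any later visit. Keep the listing. Add no separate healed-ulcer row and no p-value.
2. Reconcile the treatment-emergent windows in protocol 6.2.1.1 and SAP 8.1. If the 7-day window is kept, declare it in SAP 2.2 and tabulate later-starting events separately by arm.
3. If the sponsor prefers to keep examination data as a listing, state that in SAP 2.2 with the reason.

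The cost is a short SAP paragraph and one table from data already collected. The downside is an extra descriptive table for something that is not an endpoint, probably with small counts. The documents define no rule for a new ulcer, so the definition above should be fixed before unblinding.
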